## 3.1.1 Screening Period

At the Screening Visit, participants will be required to sign an informed consent form (ICF) before any study-related procedures are performed. After signing the ICF, participants will be assessed for study eligibility.

## 3.1.2 Treatment Period

Up to 2 weeks after the Screening Visit, participants will return to the site on Day 1 (Visit 2) and confirm study eligibility before being randomized and beginning treatment. Approximately 114 eligible participants (38 participants per treatment group) will be randomized in a 1:1:1 ratio to 1 of the following treatment groups:

- Combination therapy: Obicetrapib 10 mg + ezetimibe 10 mg (administered as one 10 mg obicetrapib tablet and one 10 mg ezetimibe capsule);
- Obicetrapib monotherapy: Obicetrapib 10 mg (administered as one 10 mg obicetrapib tablet and 1 placebo capsule); or
- Placebo (administered as 1 placebo tablet and 1 placebo capsule).

During the 12-week Treatment Period, the assigned study drugs will be administered by the participants orally with water, once daily on Day 1 to Day 84 at approximately the same time each morning. Participants will return to the site on Day 28 (±2 days), Day 84 (±2 days), and Day 112 (±2 days) for efficacy, safety, and pharmacokinetic (PK) assessments. Participants, Investigators, the Clinical Research Organization (CRO), and the Sponsor will be blinded to all lipid results from Day 1 (Visit 2) for the first participant until all enrolled participants complete the Day 84 (End of Treatment) visit or are withdrawn from the study, in order to protect blinding to treatment assignment.

## 3.1.3 Safety Follow-Up Period

Participants will return to the site for a Safety Follow-up Visit (Visit 5) approximately 4 weeks after the end of the Treatment Period for safety and PK assessments.

## 3.1.4 Coronavirus Disease 2019 Contingency Measures

In cases of COVID-19 limitations, it is the Investigator's responsibility to assure the safety of participants. If necessary, the Sponsor will implement and document mitigation strategies. At the Investigator's discretion, the study visit(s) can be conducted in-clinic or virtually. If conducted virtually, the visit will include alternative methods for safety, efficacy, and distribution/collection of study drug, including but not limited to phone/video contact, alternative location for biologic

sample collection, alternative secure delivery of study drug, home health care (if available), and a secured way of transferring participant data from and to home health services and the site.

If these contingency measures occur, the Sponsor will document the changes made, communicate recommendations about such changes in a timely fashion to minimize or prevent disruptions to the study, and support sites in implementing these changes. Documentation of these cases and the site's management of participants should be recorded in the Investigator study files. In the absence of a COVID-19 impact, it is expected that Investigators and participants follow the protocol requirements as set forth.

# 3.2 Study Indication

The indication for this study is dyslipidemia.

#### 4 SELECTION AND WITHDRAWAL OF PARTICIPANTS

## 4.1 Inclusion Criteria

Participants who meet all of the following criteria will be eligible to participate in the study:

- 1. Understanding of the study procedures, willingness to adhere to the study schedules, and agreement to participate in the study by giving written informed consent prior to screening procedures;
- 2. Men or women 18 to 75 years of age, inclusive, at the Screening Visit;
  - Women may be enrolled if all 3 of the following criteria are met:
    - They are not pregnant;
    - They are not breastfeeding; and
    - They do not plan on becoming pregnant during the study.
  - Women of childbearing potential must have a negative urine pregnancy test at the Screening Visit. Note: Women are not considered to be of childbearing potential if they meet 1 of the following criteria as documented by the Investigator:
    - They have had a hysterectomy or tubal ligation at a minimum of 1 cycle prior to signing the ICF; or
    - They are postmenopausal, defined as ≥1 year since their last menstrual period for women ≥55 years of age or ≥1 year since their last menstrual period and have a follicle-stimulating hormone (FSH) level in the postmenopausal range for women <55 years of age.

  - O Women of childbearing potential must agree to use an effective method of avoiding pregnancy from screening to 90 days after the last visit. Men whose partners are of childbearing potential must agree to use an effective method of avoiding pregnancy from screening to 90 days after the last visit. Effective methods of avoiding pregnancy are contraceptive methods with a Pearl index of <1 used consistently and correctly (including implantable contraceptives, injectable contraceptives, oral contraceptives, transdermal contraceptives, intrauterine devices, diaphragm with spermicide, male or female condoms with spermicide, or cervical cap) or a sterile sexual partner.
- 3. Fasting LDL-C levels >70 mg/dL and TG levels <400 mg/dL at the Screening Visit; and
- 4. Currently receiving high-intensity statin therapy (atorvastatin 40 or 80 mg or rosuvastatin 20 or 40 mg) at a stable dose for 8 weeks prior to screening and intending to remain at the same stable dose throughout the study duration.

## 4.2 Exclusion Criteria

Participants who meet any of the following criteria will be excluded from participation in the study:

- 1. Body mass index  $\ge 40 \text{ kg/m}^2$  at the Screening Visit;
- 2. Current clinically significant CV disease, including but not limited to:
  - Major adverse CV event within 3 months prior to randomization; or
     Note: A major adverse CV event is defined as CV death, non-fatal myocardial infarction, non-fatal stroke, or non-elective coronary revascularization.
  - o New York Heart Association Functional Classification Class III or IV heart failure.
- 3. Glycosylated hemoglobin (HbA1c) ≥10% at the Screening Visit;
- 4. Uncontrolled hypertension, ie, sitting systolic blood pressure >160 mmHg and/or sitting diastolic blood pressure >90 mmHg. One retest will be allowed, at which point if the retest result is no longer exclusionary, the participant may be randomized;
- 5. Active muscle disease or persistent creatine kinase concentration >3 × the upper limit of normal (ULN). One retest will be allowed after 1 week to verify the result, at which point if the retest result is no longer exclusionary, the participant may be randomized;
- 6. Estimated glomerular filtration rate <60 mL/min, calculated using the Chronic Kidney Disease Epidemiology Collaboration equation; 12
- 7. Hepatic dysfunction as evidenced by any laboratory abnormality as follows: gamma-glutamyl transferase, alanine aminotransferase, or aspartate aminotransferase >2 × ULN, or total bilirubin >1.5 × ULN:
- 8. Anemia, defined as hemoglobin concentration <11 g/dL for men and hemoglobin concentration <9 g/dL for women;
- 9. History of malignancy within 5 years prior to screening, with the exception of non-melanoma skin cancers;
- 10. History of alcohol and/or drug abuse within 5 years prior to screening;
- 11. Treatment with other investigational products or devices within 30 days or 5 half-lives, whichever is longer, prior to screening;
- 12. History of participation in any clinical trial evaluating obicetrapib;
- 13. Treatment with any PCSK9 inhibitor within 10 weeks prior to randomization or bempedoic acid within 2 weeks prior to randomization;
- 14. Evidence of any other clinically significant, non-cardiac disease or condition that, in the opinion of the Investigator, would preclude participant in the study; or
- 15. Known CETP inhibitor allergy or intolerance.

## 4.3 Retesting

If laboratory abnormalities during screening are considered by the Investigator to be transient, then the laboratory tests may be repeated once during screening. The Investigator's rationale for retesting should be documented. If the retest result is no longer exclusionary, the participant may be randomized.

# 4.4 Rescreening

A participant who is screened and does not meet the study eligibility criteria may be considered for rescreening upon Sponsor and/or Medical Monitor consultation and approval. Rescreened participants will be assigned a new participant number. Rescreening should occur no less than 5 days after the last Screening Visit.

#### 4.5 Withdrawal Criteria

Participation in this study may be discontinued for any of the following reasons:

- The participant withdraws consent or requests discontinuation from the study for any reason;
- Occurrence of any medical condition or circumstance that exposes the participant to substantial risk and/or does not allow the participant to adhere to the requirements of the protocol;
- Any serious AE (SAE), clinically significant AE, severe laboratory abnormality, intercurrent illness, or other medical condition, which indicates to the Investigator that continued participation is not in the best interest of the participant;
- Pregnancy;
- Requirement of prohibited concomitant medication;
- Participant failure to comply with protocol requirements or study-related procedures; or
- Termination of the study by the Sponsor or the regulatory authority.

Unless the participant withdraws consent, participants who discontinue study drug early should be encouraged to complete the full panel of assessments scheduled for the Early Termination Visit promptly and complete a Safety Follow-up Visit (Visit 5) 4 weeks after the last dose of study drug. PK samples will not be collected during the Safety Follow-up Visit for participants who discontinue study drug early without withdrawing consent or for participants who withdraw prematurely from the study. The reason for participant withdrawal must be documented in the electronic case report form (eCRF).

In the case of a participant lost to follow-up, attempts to contact the participant must be made and documented in the participant's medical records.

Withdrawn participants will not be replaced.

#### 5 STUDY TREATMENTS

# 5.1 Treatment Groups

Participants will be randomized in a 1:1:1 ratio to 1 of the following treatment groups:

- Combination therapy: Obicetrapib 10 mg + ezetimibe 10 mg (administered as one 10 mg obicetrapib tablet and one 10 mg ezetimibe capsule);
- Obicetrapib monotherapy: Obicetrapib 10 mg (administered as one 10 mg obicetrapib tablet and 1 placebo capsule); or
- Placebo (administered as 1 placebo tablet and 1 placebo capsule).

# 5.2 Rationale for Dosing

In clinical studies in healthy volunteers, obicetrapib was generally well tolerated in single doses up to 150 mg and multiple doses up to 25 mg/day for 21 days. In clinical studies in patients, obicetrapib was also well tolerated after daily dosing of 10 mg for 12 weeks, both alone and in combination with 2 different statins. Near maximal effects were observed with the 10 mg obicetrapib dose. At this dose level, CETP activity and concentrations were reduced, HDL-C levels were increased, and LDL-C levels were decreased. There were no dose-related AEs identified and no clinically significant changes in vital signs, ECGs, or hematology or biochemistry parameters in any clinical studies. A statistically significant reduction in Lp(a) levels from baseline was also observed at the 10 mg obicetrapib dose level. Therefore, the present study will utilize a dose of 10 mg obicetrapib in participants with ASCVD who are not adequately controlled despite maximally tolerated lipid-modifying therapies.

The ezetimibe dose of 10 mg is the current FDA-approved dose.

# 5.3 Randomization and Blinding

Participants who meet all eligibility criteria will be randomized into the study. Participants will be randomized in a 1:1:1 ratio to receive combination therapy (obicetrapib 10 mg + ezetimibe 10 mg [administered as one 10 mg obicetrapib tablet and one 10 mg ezetimibe capsule]), obicetrapib monotherapy (obicetrapib 10 mg [administered as one 10 mg obicetrapib tablet and 1 placebo capsule]); or placebo (administered as 1 placebo tablet and 1 placebo capsule).

At randomization, participants will be stratified according to their Screening Visit LDL-C level (≥100 or <100 mg/dL). An automated interactive response technology (IRT) system will be used to assign the participant to 1 of the 3 treatment groups.

Participants, Investigators, the CRO, and the Sponsor will be blinded to all lipid results from Day 1 (Visit 2) for the first participant until all enrolled participants complete the Day 84 (End of Treatment) visit or are withdrawn from the study, in order to protect blinding to treatment assignment.

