## **Treatment Period**

Up to 2 weeks after the Screening Visit, participants will return to the site on Day 1 (Visit 2) and confirm study eligibility before being randomized and beginning treatment. Approximately 114 eligible participants (38 participants per treatment group) will be randomized in a 1:1:1 ratio to 1 of the following treatment groups:

- Combination therapy: Obicetrapib 10 mg + ezetimibe 10 mg (administered as one 10 mg obicetrapib tablet and one 10 mg ezetimibe capsule);
- Obicetrapib monotherapy: Obicetrapib 10 mg (administered as one 10 mg obicetrapib tablet and 1 placebo capsule); or
- Placebo (administered as 1 placebo tablet and 1 placebo capsule).

During the 12-week Treatment Period, the assigned study drugs will be administered by the participants orally with water, once daily on Day 1 to Day 84 at approximately the same time each morning. Participants will return to the site on Day 28 (±2 days), Day 84 (±2 days), and Day 112 (±2 days) for efficacy, safety, and pharmacokinetic (PK) assessments. Participants, Investigators, the Clinical Research Organization, and the Sponsor will be blinded to all lipid results from Day 1 (Visit 2) for the first participant until all enrolled participants complete the Day 84 (End of Treatment) visit or are withdrawn from the study, in order to protect blinding to treatment assignment.

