#### **8.1** Adverse Events

An AE is defined as any untoward medical occurrence in a clinical investigation participant administered a pharmaceutical product, which does not necessarily have a causal relationship with this treatment. An AE can therefore be any unfavorable and/or unintended sign (including an abnormal laboratory finding), symptom, or disease temporally associated with the use of an investigational medicinal product, whether or not related to the investigational medicinal product. All AEs, including observed or volunteered problems, complaints, or symptoms, are to be recorded on the appropriate eCRF.

AEs, which include clinical laboratory assessment variables, will be monitored and documented from the time of first dose of study treatment until completion of Visit 5. Participants should be instructed to report any AE that they experience to the Investigator, whether or not they think the event is due to study drug. Beginning at the date of the first dose of study treatment, Investigators should make an assessment for AEs at each visit and record the event on the appropriate AE eCRF.

Wherever possible, a specific disease or syndrome rather than individual associated signs and symptoms should be identified by the Investigator and recorded on the eCRF. However, if an observed or reported sign or symptom is not considered a component of a specific disease or syndrome by the Investigator, it should be recorded as a separate AE on the eCRF. Additionally, the condition that led to a medical or surgical procedure (eg, surgery, endoscopy, tooth extraction, or transfusion) should be recorded as an AE, not the procedure itself.

Any medical condition already present at the date of the first dose of study treatment should be recorded as medical history and not be reported as an AE unless the medical condition or signs or symptoms present at baseline changes in severity, frequency, or seriousness at any time during the study. In this case, it should be reported as an AE.

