## 8.1.3 Assessment of Adverse Events by the Investigator

The Investigator will assess the severity (intensity) of each AE as mild, moderate, or severe, and will also categorize each AE as to its potential relationship to study drug using the categories of yes or no.

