2.2 Study Design

2.2.1 Overview

This study is a placebo-controlled, double-blind, randomized, Phase 2 study to evaluate the efficacy, safety, and tolerability of obicetrapib 10 mg, both in combination with ezetimibe 10 mg and as monotherapy, as an adjunct to high-intensity statin therapy.

Approximately 114 eligible participants (38 participants per treatment group) will be randomized in a 1:1:1 ratio to 1 of the following treatment groups:

- Combination therapy: Obicetrapib 10 mg + ezetimibe 10 mg (administered as one 10 mg obicetrapib tablet and one 10 mg ezetimibe capsule);
- Obicetrapib monotherapy: Obicetrapib 10 mg (administered as one 10 mg obicetrapib tablet and 1 placebo capsule); or
- Placebo (administered as 1 placebo tablet and 1 placebo capsule).

Randomization will be stratified according to LDL-C levels (≥ 100 or < 100 mg/dL).

During the 12-week Treatment Period, the assigned study drugs will be administered by the participants, once daily on Day 1 to Day 84 at approximately the same time each morning. Participants will return to the site on Day 28 (± 2 days), Day 84 (± 2 days) and Day 112 (± 2 days) for efficacy, safety, and pharmacokinetic (PK) assessments. Participants, Investigators, and the Clinical Research Organization (CRO), and the Sponsor will be blinded to all lipid results from Day 1 (Visit 2) for the first participant until all enrolled participants complete the Day 84 (End of Treatment [EOT]) visit or are withdrawn from the study, in order to protect blinding to treatment assignment.

Participants will return to the site for a Safety Follow-Up (FUP) Visit (Day 112; Visit 5) approximately 4 weeks after the end of the Treatment Period for safety and PK assessments.

Refer to [Table 1 Schedule of Procedures](#) for further details.

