3.6.1 Adverse Events (AEs)

AEs will be categorized by primary system organ class and preferred term as coded using the MedDRA (version 24.1) category designations.

An overview of treatment-emergent AEs (TEAEs) will be provided including counts and percentages of participants (and event counts) with the following:

- Any TEAEs overall and by maximum severity
- Any study drug related TEAEs, overall and by maximum severity
- Any TEAEs leading to discontinuation of study drug
- Any treatment-emergent serious AEs (TESAEs)
- Any study drug related TESAEs
- Any TEAEs leading to death

The TEAEs described above will be summarized separately by System Organ Class and Preferred Term.

Listings will be presented specifically for TEAEs, TESAEs and TEAEs leading to discontinuation of study drug.

3.6.2 *Clinical Laboratory Tests*

Blood for chemistry and hematology will be obtained as indicated in Table 1 Schedule of Procedures and sent to a central laboratory for analysis. See Appendix A for a complete list of analytes. Blood samples for chemistry and hematology must be obtained under fasting conditions (i.e., after the participant has fasted for ≥ 10 hours).

Laboratory values will be summarized descriptively, including the change and percent change from baseline. In addition, shift tables will be presented to describe the change in laboratory parameter values at post-baseline visits using normal range categories (low, normal, and high).

All safety laboratory data will be presented in participants listings.

3.6.3 *Vital Signs*

Vital signs including body temperature, heart rate, and triplicate blood pressure will be measured at all scheduled visits. Triplicate blood pressure measurements will be averaged for analysis.

Values and changes from baseline will be summarized with descriptive statistics at each visit.

Separate plots will be provided for the change from baseline in systolic and diastolic blood pressure by visit.

Height and weight will be measured at the Screening Visit only. Body Mass Index (BMI) will be derived as weight/(height/100)² (kg/m²); rounded and displayed to 1 decimal place.

3.6.4 *Electrocardiograms*

A single, standard 12-lead ECG will be performed on-site at the Screening Visit and read locally.

ECG data will be summarized with descriptive statistics and presented in participant listings.

3.6.5 *Physical Examinations*

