4.2 Pre-Final Analysis

After the database is locked and exclusions from analysis populations have been finalized, the randomized treatment assignments will be unblinded and the pre-final analysis will be generated. Pre-final tables, figures, and listings (TFLs) will be provided approximately 3 weeks after database lock.

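### Minor, cheap improvement: lipid results may be released after the last Day 84 visit, before the last safety visit and database lock, although masking them is meant to protect the treatment blind

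*Protocol*

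**What the plan says.** Four places give the same rule: the Protocol Synopsis (Treatment Period), Protocol 3.1.2, Protocol 5.3 and SAP 2.2.1. Protocol 5.3 keeps participants, investigators, the CRO and the sponsor "blinded to all lipid results from Day 1 (Visit 2) for the first participant until all enrolled participants complete the Day 84" visit or are withdrawn. Protocol 3.1.2 runs the masking "until all enrolled participants complete the Day 84 (End of Treatment) visit or are withdrawn from the study". SAP 2.2.1 has the same end point: "until all enrolled participants complete the Day 84 (End of Treatment [EOT]) visit or are withdrawn from the study". The Synopsis shows the end point and its reason together: "visit or are withdrawn from the study, in order to protect blinding to treatment assignment".

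The treatment codes have a later end point. SAP 4.2 states: "After the database is locked and exclusions from analysis populations have been finalized, the randomized treatment assignments will be unblinded".

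Three kinds of judgement can still be open between these two points:

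- **Adverse events.** Under Protocol 8.1 they "will be monitored and documented from the time of first dose of study treatment until completion of Visit 5". Under Protocol 8.1.3 the investigator "will also categorize each AE as to its potential relationship to study drug using the categories of yes or no". SAP 3.6.1 tabulates the result: "Any study drug related TEAEs, overall and by maximum severity".
- **Per-protocol exclusions.** These must be final before study unblinding (Protocol Synopsis and 9.1, SAP 3.2.3).
- **The SAP.** It must be final before database lock (Protocol Synopsis and 9.2, SAP 1). Protocol 7.1 collects LDL-C in two ways at Visits 2 and 4 without saying which feeds the primary analysis. SAP 3.4.1 makes that choice.

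Neither deadline is tied to the release of lipid results, and no section extends lipid masking to Visit 5 or to lock.

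**The concern.** A safeguard whose purpose is to protect the treatment blind should last as long as the blind. Here it can end sooner. The drug under test changes lipids markedly, so a person who sees a participant's values can make an informed guess at the assignment while the codes are still formally closed.

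At stake are decisions made by people rather than by the laboratory. They are the yes/no causality call for adverse events in participants still in follow-up, the late per-protocol exclusions, and any analysis choice left until the SAP is signed. The choice of LDL-C measure belongs in the last group and bears on the primary endpoint.

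**Working it through.** **1. The plan's own figure (a check of inputs only).** Protocol 9.2.5 gives a 30-point difference, SD 15, 36 evaluable per group, 1-sided alpha 0.025 and power above 90%. The standard error is 15 × √(2/36) = 3.54, and 30/3.54 = 8.5, so power exceeds 99.9% and the stated figure is met. Dropout: 36/0.95 = 37.9, giving 38 per group and 114 in all, as stated. The point does not depend on these figures.

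**2. Length of the interval.** From the visit windows in Protocol 3.1.2, Day 84 falls on Days 82 to 86 and Visit 5 on Days 110 to 114.

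- Shortest: 110 − 86 = 24 days.
- Longest: 114 − 82 = 32 days.
- Nominal: 112 − 84 = 28 days.

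The same bounds hold between the trial's last Day 84 visit and its last Visit 5, provided the last participants complete both in window. If the last open participant is instead withdrawn, Visit 5 is timed from the last dose (Protocol 4.5) and the gap can differ. The time from Visit 5 to lock comes on top. That lock follows the last Visit 5 is inferred from Protocol 10.3 and SAP 4.2; no lock date is given.

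**3. How far LDL-C reveals assignment.** Cut at the midpoint between the placebo and obicetrapib means. The share classified correctly is Φ(difference / (2 × SD)).

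- SD 15 (Protocol 9.2.5): Φ(30/30) = Φ(1.00) = 84%.
- SD 20 (assumed): Φ(30/40) = Φ(0.75) = 77%.
- SD 25 (assumed): Φ(30/50) = Φ(0.60) = 73%.
- Benchmark: always guessing obicetrapib under 1:1:1 allocation is right in 2/3 = 67%.

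This assumes normal distributions, equal SDs, the same mean in both obicetrapib groups, and a reader who knows where to cut. HDL-C would probably add information, since Protocol 1.3 reports a 179.0% rise in an earlier study, but no SD is given and it is left out.

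**4. How much follow-up is exposed.** Accrual time is not stated, so uniform accrual over A days is assumed, with no dropout. Participants still in follow-up at the last Day 84 visit number 114 × 28/A. Their remaining follow-up, as a share of all planned adverse event observation time, is (28²/2)/(112 × A) = 3.5/A.

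| Assumed accrual | Still in follow-up | Share of observation time |
|---|---|---|
| 3 months (91.3 days) | 35 | 3.8% |
| 6 months (182.6 days) | 17 | 1.9% |
| 12 months (365.25 days) | 9 | 1.0% |

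This does not count late queries on earlier events, or the causality call that decides whether a serious event more than 30 days after the last dose is reported (Protocol 8.3).

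**The case against.** The case for leaving the rule alone is strong on size. The four statements agree with one another. They say when masking may end and do not instruct anyone to circulate results. By then all Day 84 samples have been drawn, and Protocol Appendix A schedules no lipid profile at Visit 5. Codes stay closed to lock, individual unblinding is restricted (Protocol 5.4), and deviations follow a separate plan (SAP 3.3.2). The protocol fixes the main model terms and the testing order (9.2.1.1, 9.2.1.2). Safety is descriptive (9.2.3) and the per-protocol analysis is supportive (9.2.1). All of this stands, and it is why the point is minor. It does not bring the end of masking into line with its stated purpose.

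A second objection concerns the remedy. Holding every lipid value at the laboratory until lock would remove the sponsor's and CRO's review of downloaded data (Protocol 10.1.5) for the primary variable, which has a conditional calculation rule (SAP 3.4). That would be a poor trade, so the fix below does not ask for it.

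A reader might infer from SAP 5 that analyses were changed after results were seen: the lowest LDL-C target moved from 50 to 55 mg/dL, HDL-ApoE was dropped, and particle and PCSK9 endpoints were added. The documents do not support this. The changes are all exploratory, two carry stated reasons (a guideline target and an invalid assay), and none is dated against any lipid release. The same holds for the choice of LDL-C measure in SAP 3.4.1.

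**Conclusion.** The point holds as a minor, cheap improvement. The plan allows lipid masking to lapse before the blind it protects, by 24 to 32 days plus the time to lock when the last participants attend in window. In that period LDL-C change alone could classify about 84% of participants correctly on the protocol's SD, and 73% to 77% on the larger assumed SDs. The gain over the 67% benchmark therefore runs from modest to substantial, depending on an SD the trial has yet to show.

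A reader might go further and conclude that the study is unblinded at Day 84 or that the primary result is compromised. The documents do not support either. Primary endpoint measurement is untouched and the codes remain closed. The exposure is confined to late causality calls, per-protocol exclusions and SAP choices not yet settled. The documents do not show that any result was released or seen early.

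**What to change.** 1. **Sites.** In the Protocol Synopsis (Treatment Period), Protocol 3.1.2, Protocol 5.3 and SAP 2.2.1, leave the start of masking as it is. Keep participants and investigators masked to all post-randomization lipid results until database lock and treatment unblinding. Word any site query without the value. Individual unblinding under Protocol 5.4 is unchanged.
2. **Sponsor and CRO.** In the Protocol Synopsis (Statistical Analyses and Analysis Populations), Protocol 9.1 and 9.2, and SAP 1 and 3.2.3, require the SAP and the per-protocol list to be final and dated before any lipid result is released to the sponsor or CRO. They may then review lipid values for data cleaning before lock. The per-protocol rule needs only to know that a Day 84 LDL-C value exists, which the laboratory can report as a status.
3. **Other revealing results.** Apply the same masking to Lp(a), PCSK9 and plasma obicetrapib concentrations. The present rule speaks only of lipid results, and no section says how the concentrations are masked.

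The cost is wording edits plus a result-release instruction. Sites receive lipid values some weeks later, as do personal physicians when participants ask for them to be sent (Protocol 11.5). The SAP and per-protocol list must be finished sooner. N, power, visits and the model do not change.
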